AF-FLOW Registry

A post market, global registry to evaluate the identification of Atrial Fibrillation sources using the Ablamap Electrographic FLOW (EGF) Mapping System to guide ablation therapy in patients with Atrial Fibrillation

Sponsor: Ablacon, Inc.

Business Address: [name]
[name]

Protocol No: CP-003

Date: May 3, 2022

Product: Ablamap® Electrographic Flow Software

Revision Number: REV A

Sponsor Contact: [name]
Ablacon, Inc.
[contact]
[contact]

Principal Investigator: [name], Piedmont Athens Hospital
[name], Southlake Regional Health Center

Study Management: Ablacon, Inc.

CONFIDENTIAL: The contents of this document are proprietary and confidential. This protocol contains valuable engineering, clinical and commercial information which must not be disclosed to potential competitors. Duplication and distribution of this document requires prior approval from Sponsor.

PROTOCOL SUMMARY

Objective	This post-market global registry will evaluate the ability of the Ablamap® Software to identify atrial fibrillation sources and guide ablation therapy in patients with atrial fibrillation
Test Device	Ablacon Electrographic Flow (EGF) algorithm technology (Ablamap® Software)
Study Design	Post-market, prospective, multi-center, global registry
Planned Subject Sample Size	Up to 100 subjects
No. of Sites	Subjects will be enrolled at up to ten (10) investigational sites in Europe and United States
Primary Efficacy Endpoint	Acute procedure success defined as the ability to successfully ablate AF sources identified by the Ablamap Software
Secondary Efficacy Endpoints	Freedom from documented episodes of AF recurrence following the blanking period (90 days post-ablation) through 12 months
Inclusion Criteria	
1. Suitable candidate for intra-cardiac mapping and ablation of arrhythmias.2. Above eighteen (18) years of age or of legal age to give informed consent specific to state and national law.3. Subjects with a history of documented symptomatic atrial fibrillation.
Exclusion Criteria	
1. Subjects who are not candidates for cardiac ablation procedures.2. Pregnant or nursing.3. Presence of anatomic or comorbid conditions, or other medical, social or psychological conditions that, in the investigator's opinion, could limit the subject's ability to participate in the clinical investigation or comply with follow-up requirements.

Follow-Up Schedule

1. INTRODUCTION

[figure not shown]
Atrial fibrillation (AF) is the most common cardiac arrhythmia and is associated with increased mortality, morbidity and impaired quality of life. Catheter ablation has become the standard of care for symptomatic patients with drug-refractory AF and the cornerstone of ablation remains the electrical isolation of the pulmonary veins (pulmonary vein isolation = PVI).¹ For patients with paroxysmal AF, long-term effectiveness of an approach based on PVI as the sole ablation strategy is reported to be 81.6% at 12 months, 73.8% at 24 months, and 68.1% at 36 months post-ablation.² However, the success rate of PVI for patients with persistent AF is significantly lower with rates of freedom from AF at 12 months post-ablation ranging from 51 up to 60% regardless of the catheter ablation strategy, addition of antiarrhythmic drugs, use of cryoballoon v. RF ablation, or lesion set performed.³⁻⁶ This ceiling of efficacy in the persistent AF population may be attributable to the complex functional mechanisms of AF contributing to an individual patient's disease state.

Beyond the pulmonary vein triggers, the development and persistence of AF depends upon a localized source—a trigger or driver as well as susceptible substrate, such as re-entrant circuits and or regions of fibrotic atrial myocardium with abnormal conduction properties.^{1,7,8} After pulmonary vein isolation has been performed, accurate, enhanced mapping techniques that can localize extra-PV drivers/triggers is needed to further guide the next step in the ablation strategy.

Efforts to hone in on AF mechanisms underlying persistent AF have multiplied and several different methods for identifying these localized sources have been put forth using global or panoramic mapping techniques.⁹⁻¹² However, due to the chaotic nature of the intracardiac electrograms (EGMs) characteristic of AF, identifying active focal sources relevant to the initiation and maintenance of AF has remained challenging.

Electrographic Flow (EGF) Mapping (Ablamap® Software, Ablacon, Wheat Ridge, CO) is an innovative technique to create full temporospatial visualizations of organized cardiac action potential flow within the chaotic conduction of AF that can discriminate between active sources of excitation and passive rotations, which do not generate action potentials; and can estimate the average activity of such a source during a time interval such as one minute.¹¹ It has been shown that only those sources that are generating excitation and that are active more than a quarter of the time are significant predictors for AF recurrence after PVI.¹² Using a 64-electrode basket mapping catheter, the software collects unipolar intracardiac EGMS. These EGMS are then processed using a proprietary algorithm employing Green's energy-optimizing formula to create a smooth landscape of voltage potentials for each sample point in time. An optical flow mapping algorithm is then applied to assemble these snapshots into a continuous recording of the excitation waves' behavior and propagation over time. The software also displays the dominant patterns of the excitation wave propagation recordings as vector flow maps, whose consistency over time can be measured and statistically analyzed (Figure 1):

Figure 1: Methodology of EGF Mapping

Ablacon has recently completed enrollment in the first randomized, controlled, clinical study to evaluate the Ablamap Software (FLOW-AF Study, NCT: NCT04473963). A total of 85 subjects were enrolled across four European centers. All subjects are being followed through twelve months, and the results will be available in late 2022.

The goal of this registry is to continue to evaluate the Electrographic Flow mapping software for identifying AF sources in patients to optimize ablation success in a real-world setting.

2.1 Test Device Description

The Ablamap Software is an electrophysiological mapping software application designed to analyze the flow of excitation in cardiac tissue. The software uses an optical flow algorithm to process recorded files of electrocardiogram (ECG) signals from multiple-electrode mapping catheters (e.g., basket catheters) by transforming the time domain waveform information from all electrodes into space domain information and calculating velocity vectors of the electrographic action potential flow (EGF) for each point in space.

The output is a set of files that graphically depict flow directions (velocity vectors) and sources where the flow is generated. The software discriminates between sources that may be focal or rotational and passive rotations that are not sources; detects spatial and temporal stability of sources; and defines the activity of sources as the percentage of time a source is at its maximum stability.

The Ablamap Software is stand-alone software installed on a standard, commercially available desktop or laptop computer. The software processes ECG data files that have been saved on a USB memory device, the computer, or a data server. The software does not control or interface with any medical device. There is no user or patient contact.

2.2 Justification of Trial Design

The AF-FLOW Registry is a global post-market registry being conducted to collect clinical data to further characterize the performance of the Ablamap Software for its intended use. We also intend to continue to clinically validate the ability of the Ablamap Software to identify AF sources and guide ablation therapy in patients with atrial fibrillation.

2.3 Indications for Use

The Ablamap Software is used to analyze intra-cardiac electrogram (EGM) signals and display results in a visual format for evaluation by a physician in order to assist in the diagnosis of complex cardiac arrhythmias.

2.4 Intended Use

The Ablamap Software is intended to be used during electrophysiology procedures on patients for whom an electrophysiology procedure has been prescribed and only by qualified medical professionals trained in electrophysiology.

The Ablamap Software is CE-marked and FDA 510(k) cleared for use in the EU and United States.

2.5 Potential Risks and Benefits

2.5.1 Anticipated Risks associated with the Ablamap Software

There are no patient or user safety issues or hazards identified for the Ablamap Software in the clinical data analyzed within a comprehensive literature review and the FLOW-AF Clinical Study. Internal data generated as part of the risk analysis of the Ablamap Software indicates there were no patient or user safety issues or hazards identified.

The Ablamap Software Safety Classification per BS EN 62304:2006+A1:2015 is Safety Class A where the hazard probability is *Improbable* and the hazard severity is *Negligible*.

Current market experience shows no evidence to suggest that the Ablamap Software poses any safety issues or any hazards and there are no safety issues or hazards that outweigh the benefits of the system.

2.5.2 Risks Associated with Participation in the Clinical Study

There is no foreseen increased risk to subjects for participating in the clinical study.

2.5.3 Anticipated Benefits

The benefit to the subjects enrolled in this study is the potential for improved judgement by the clinician due to the additional information provided by the Ablamap software. Specifically, the software analyses will guide and support physicians to enable targeted ablation techniques that may improve acute and long-term clinical outcomes.

3. STUDY PROTOCOL

3.1 Objective

The objective of this global post-market registry is to obtain clinical data in order to further characterize the performance of the Ablamap System for its intended use. Specifically, we will evaluate the ability of the Ablamap Electrographic Flow (EGF) System to identify AF sources and guide ablation therapy in patients with atrial fibrillation.

3.2 Study Endpoints

- Primary Efficacy Endpoint: Acute procedure success defined as the ability to successfully ablate AF sources identified by the Ablamap Software.
- Secondary Efficacy Endpoint: Freedom from documented episodes of AF recurrence following the blanking period (90 days post ablation) through 12 months.

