3.6 Statistical Analysis

The primary efficacy endpoint of this registry is the successful elimination of significant sources of excitation. Target parameter is the activity of the leading source. According to the retrospective data analyzed previously, the critical threshold for significance of a source is an activity of 26%.

Significance of the leading source will be tested in each patient at multiple times, in every procedure performed, in both atria, before and after PVI or PV touch-up and before and after ablation. The effect of targeted ablation will be statistically analyzed by determining the rate of reduction of leading source activity below threshold upon ablation. If an ablation is not successfully reducing the activity or if the location of the leading source changes upon ablation, ablation will be repeated.

The secondary endpoint of the study is freedom from documented episodes of AF recurrence following the blanking period (90 days post ablation) through 12 months.

We will analyze the level of significance of this difference based on the patients with sources above threshold that were successfully ablated and remained AF free versus those patients where no sources or sources below threshold were seen but were not ablated.

Descriptive summary statistics for continuous variables will include the number of subjects, mean, standard deviation or standard error, median, minimum, and maximum. Nominal categorical variables will be summarized using counts and percentages. Ordinal variables may be analyzed as if they were continuously scaled. Subject disposition, the number and percentage of subjects who complete and discontinue as well as reasons for early discontinuation will be presented. Demographic and baseline characteristics will be summarized descriptively.

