5.7 Follow-up Visits

Investigators should follow their standard practices for following subjects post ablation. The AF-FLOW Registry will formally collect baseline demographics, medical history, ablation procedural data and 12-month follow-up visit data.

If a subject returns at any time within the 12-month follow-up period with evidence of AF recurrence, the data will be collected on an Unscheduled Visit CRF.

5.7.1 12-Month Follow-Up

All subjects must be evaluated at twelve months (365 +/- 45 days) after the index ablation procedure.

During this follow-up, the following will be performed:

- Any previously unreported AF recurrences since the index ablation procedure (or cardioversion or repeat ablation procedure for previous AF recurrence).
- Any medication changes (AADs, anticoagulants, and other cardiac medications)
- Perform a 12-lead ECG
- Complete the Study Completion CRF

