5.12 Adverse Event Reporting

An adverse event (AE) is any untoward medical occurrence in a subject. All adverse events are to be reported on the Adverse Event Case Report Form. All adverse events will be documented with the date of occurrence, relatedness to device or procedure, severity, action taken, resolution and any pertinent additional information.

Adverse events will be reported and classified by the investigator from the medical diagnosis, using clinical signs, symptoms or abnormal laboratory values as needed. The investigator will classify the adverse events based on the definitions as follows (ISO 14155:2011).

Term	Definition
Adverse event (AE):	Any untoward medical occurrence, unintended disease or injury, or untoward clinical signs (including abnormal laboratory findings) in subjects, users or other persons, whether or not related to the test device.
Adverse device effect (ADE):	Adverse event related to the use of a test device.
Serious adverse event (SAE):	
Is an adverse event that:
 

led to a death,
led to serious deterioration in the health of the subject, that either resulted in,

a life-threatening illness or injury or,
a permanent impairment of a body structure or a body function or,
an in-patient or prolonged hospitalization or,
a medical or surgical intervention to prevent life-threatening illness or injury or permanent impairment to a body structure or a body function. 
NOTE: Planned hospitalization for a pre-existing condition, or a procedure required

Term	Definition
	by the clinical investigational plan, without serious deterioration in health, is not considered a serious adverse event.
Serious adverse device effect (SADE):	Adverse device effect that has resulted in any of the consequences characteristic of a serious adverse event.
Unanticipated serious adverse device effect (USADE):	Serious adverse device effect which by its nature, incidence, severity or outcome has not been identified in the current version of the risk analysis report. NOTE: Device deficiencies include malfunctions, use errors, and inadequate labeling.

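### The 12-month endpoint and the recurrence forms cover AF only, so a subject who returns with only atrial flutter or atrial tachycardia can be counted as recurrence-free

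*Combined protocol and SAP*

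**What the plan says.** Section 3.2 defines the secondary endpoint as "Freedom from documented episodes of AF recurrence following the blanking period (90 days post ablation) through 12 months". Section 3.6 keeps the same scope: "The secondary endpoint of the study is freedom from documented episodes of AF recurrence". The term AF recurrence is not defined, and neither atrial flutter nor atrial tachycardia is mentioned anywhere in the document.

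Recurrence data reach the registry by two dedicated routes, both in section 5.7. If a subject comes back during follow-up "with evidence of AF recurrence, the data will be collected on an Unscheduled Visit CRF". At 12 months the site asks about "Any previously unreported AF recurrences since the index ablation procedure". The follow-up schedule in the Protocol Summary likewise ties unscheduled visits to AF.

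Two general routes exist alongside these. The 12-month visit includes the instruction "Perform a 12-lead ECG", and section 5.12 states "All adverse events are to be reported on the Adverse Event Case Report Form". Neither is connected to the endpoint.

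Section 3.6 contains the plan's only between-group comparison: "patients with sources above threshold that were successfully ablated and remained AF free versus those patients where no sources", or only below-threshold ones, were found and no ablation of them was done. Under section 5.5, pulmonary vein isolation (PVI) is completed or verified in everyone before the EGF maps that decide on source ablation.

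**The concern.** A subject with flutter or tachycardia after day 90, but no documented AF, meets no stated failure criterion. Two consequences follow.

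First, the reported freedom figure may be read as freedom from atrial arrhythmia when it is not. Any flutter-only or tachycardia-only return makes AF-only freedom the larger of the two. This does not depend on how the groups compare.

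Second, the two groups in 3.6 differ in the lesions they receive at the index procedure. Taking 3.6 at its word, the comparator was not ablated beyond PVI, so the additional lesions fall in the source-ablated group alone. If those subjects have more flutter-only or tachycardia-only returns, the endpoint leaves out more of their recurrences than of the comparator's, and the difference moves in favour of source ablation.

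Follow-up otherwise runs on each site's usual practice, with one formal visit. Rhythm type that is not collected prospectively may be hard to recover later.

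**Working it through.** **Which route leads to the endpoint**

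| Route | Section | Scope | Tied to the endpoint? |
|---|---|---|---|
| Unscheduled Visit CRF | 5.7 | AF recurrence | Yes, by subject matter |
| 12-month recurrence question | 5.7.1 | AF recurrence | Yes, by subject matter |
| 12-month ECG | 5.7.1 | Any rhythm, one time point | No rule for a non-AF atrial arrhythmia |
| Adverse Event CRF | 5.12 | Any adverse event | No rule |

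So a flutter or tachycardia episode can be recorded, but no rule turns it into a recurrence.

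**Size.** The plan gives no flutter or tachycardia rate, significance level, power or group split, so there is no figure of its own to reproduce. Let F_AF be freedom from AF, F_any freedom from AF, flutter or tachycardia, and a the share of a group with flutter or tachycardia but no AF after day 90. Then

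F_AF = F_any + a

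and for groups 1 (source-ablated) and 2 (comparator)

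(F_AF,1 − F_AF,2) − (F_any,1 − F_any,2) = a1 − a2.

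The artificial difference is a1 − a2, whatever the true freedom is. Assumed ranges: a1 = 5-15%, a2 = 2-5%. Freedom is then overstated by 5-15 points in group 1 and 2-5 points in group 2. All four corners must be considered:

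| a1 | a2 | Artificial difference |
|---|---|---|
| 5% | 5% | 5 − 5 = 0 points |
| 5% | 2% | 5 − 2 = 3 points |
| 15% | 5% | 15 − 5 = 10 points |
| 15% | 2% | 15 − 2 = 13 points |

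The range is 0 to 13 points.

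**What that could do to a test.** Further assumptions: F_any is equal in both groups, at 51% or 60% (the persistent-AF range for freedom from AF in section 1, used as a stand-in); a two-sided 5% test; 100 subjects split 50/50 or 70/30. The chance of a significant result favouring group 1 is

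Φ[(d − 1.96·SE0) / SE1],

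with d the artificial difference, SE0 the pooled and SE1 the unpooled standard error. Example with d = 13 points, F_any = 51%, 50/50: apparent freedom is 66% versus 53%, SE0 = 0.0982, SE1 = 0.0973, so Φ[(0.13 − 0.1924)/0.0973] = Φ(−0.64) = 26%.

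| Artificial difference | Chance of a false result favouring group 1 |
|---|---|
| 0 points (5% v 5%) | 2.5% |
| 3 points (5% v 2%) | about 5% |
| 10 points (15% v 5%) | 16-19% |
| 13 points (15% v 2%) | 24-29% |

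For scale, 50 versus 50 subjects give 80% power only for a true difference of about 25-27 points.

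**A limit on this arithmetic.** It treats the comparison as one of two freedom rates. As written, group 1 consists of "patients with sources above threshold that were successfully ablated and remained AF free", so its AF freedom is 100% by construction. Changing the endpoint alone does not cure that: composite freedom in group 1 would still be measured only among subjects already known to be free of AF. The figures above apply only once that condition is removed.

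**The case against.** The strongest reply is that AF freedom is a coherent endpoint for a device meant to find AF sources. Section 1 benchmarks persistent AF on the same measure, and this is a secondary endpoint in a post-market registry of up to 100 subjects. That stands, and it is why AF freedom should be kept.

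A reader might infer that the case report forms cannot record flutter or tachycardia at all. The documents do not support that. Adverse event reporting is general. Section 5.12 takes hospitalisations for recurrent AF out of the adverse events but makes no such exception for flutter or tachycardia. It also mentions the Unscheduled Visit CRF for a recurrence without repeating AF, although the sentence before it concerns recurrent AF. What remains is that no rule carries such a record to the endpoint.

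A reader might also infer that every such subject will be scored a success. Since AF recurrence is undefined, sites may code these rhythms either way. That is inconsistent classification rather than demonstrated systematic relabelling, and a rhythm field addresses both.

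The most tempting inference is that the comparison is biased toward source ablation as a matter of fact. The documents say nothing on whether lesions outside the pulmonary veins change the frequency of these rhythms. With equal rates the difference is unbiased. Pairing the low ends and the high ends of the assumed ranges would suggest 3 to 10 points and hide that the same assumptions allow zero.

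The contrast in lesions also depends on reading the comparator literally. Section 5.5 lets investigators ablate subjects without above-threshold sources by their usual practice. If those subjects were counted in the comparator, the contrast would weaken. Redo subjects may also bring earlier lesions into either group.

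**Conclusion.** The concern holds in limited form. The endpoint and both dedicated recurrence routes are confined to AF, and a subject with only flutter or tachycardia can be counted as recurrence-free. AF-only freedom can therefore exceed freedom from atrial arrhythmia. The 3.6 difference can favour the source-ablated group, but only if such rhythms are more frequent there.

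The size, 0 to 13 points, rests entirely on the assumed 5-15% and 2-5%. The false-positive figures rest further on equal true freedom, the stand-in range of 51-60%, a two-sided 5% test and the assumed splits.

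The larger fault in the same comparison is that the source group is selected on its outcome. The groups are also not randomised and differ in source status, so even a corrected comparison would not isolate the effect of ablation.

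**What to change.** 1. Keep freedom from AF as stated.
2. Widen the Unscheduled Visit CRF trigger and the 12-month question to AF, atrial flutter or atrial tachycardia, and add a field for the documented rhythm.
3. Co-report freedom from any of the three after day 90 through 12 months, overall and in the 3.6 comparison.
4. Define both 3.6 groups by source and ablation status only, and drop the condition of having remained AF-free. Without this step neither endpoint gives a valid comparison.

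The cost is one CRF field, a wider trigger and question, one more table and a reworded group definition. No treatment rule changes. The downside for the sponsor is that the composite freedom figure will be the same as or lower than AF-only freedom.
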